## 3.2 Exclusion Criteria

3.2.1 Chemotherapy-related or radiation-related toxicities that have not resolved to Grade 1 severity or lower, except for stable sensory neuropathy ( $\leq$  Grade 2) and alopecia.

3.2.2 Participants who are receiving any other investigational agents.

- 3.2.3 Previous treatment with eribulin mesylate or any anti-PD-1, PD-L1, or PD-L2 agent or participation in any MK-3475 Merck studies.
- 3.2.4 History of allergic reactions attributed to compounds of similar chemical or biologic composition to eribulin mesylate or pembrolizumab.
- 3.2.5 Known brain metastases that are untreated, symptomatic, or require therapy to control symptoms. Participants with previously diagnosed brain metastases are eligible if they have completed treatment at least 4 weeks prior to registration, are neurologically stable and absence of new neurologic symptoms for the last 4 weeks prior to study entry, and have recovered from the effects of radiotherapy or surgery. Any corticosteroid use for brain metastases must have been discontinued without the subsequent appearance of symptoms for  $\geq 2$  weeks before the first study drug. Treatment for brain metastases may have included whole brain radiotherapy, radiosurgery, or a combination as deemed appropriate by the treating physician.
- 3.2.6 Uncontrolled intercurrent illness, including, but not limited to uncontrolled hypertension, unstable angina pectoris, uncontrolled cardiac arrhythmia, congestive heart failure-New York Heart Association Class III or IV, active ischemic heart disease, myocardial infarction within the previous six months, uncontrolled diabetes mellitus, gastric or duodenal ulceration diagnosed within the previous 6 months, chronic liver or renal disease, severe malnutrition or psychiatric illness/social situations that would limit compliance with study requirements.
- 3.2.7 Clinically significant electrocardiogram (ECG) abnormality, including a marked baseline prolonged QT/QTc ([QT interval/corrected QT interval], eg, a repeated demonstration of a QTc interval  $>500$  ms).
- 3.2.8 Medicinal condition that requires chronic systemic steroid therapy or on any other form of immunosuppressive medication. For example, participants with autoimmune disease that requires systemic steroids or immunosuppression agents should be excluded. Replacement therapy (eg., thyroxine, insulin, or physiologic corticosteroid replacement therapy for adrenal or pituitary insufficiency, etc.) is not considered a form of systemic treatment.
- 3.2.9 History or evidence of active, noninfectious pneumonitis that required treatment with steroids.
- 3.2.10 History of interstitial lung disease.
- 3.2.11 Participants known to be positive for the human immunodeficiency virus (HIV), Hepatitis B antigen (HepBsAg), or Hepatitis C virus (HCV) RNA. HIV-positive participants on combination antiretroviral therapy are ineligible because of the potential for pharmacokinetic interactions with Pembrolizumab and/or eribulin mesylate. In addition, these participants are at increased risk of lethal infections.

3.2.12 Individuals with a history of a second malignancy are ineligible except for the following circumstances. Individuals with a history of other malignancies are eligible if they have been disease-free for at least 5 years and are deemed by the investigator to be at low risk for recurrence of that malignancy. Individuals with the following cancers are eligible if diagnosed and treated within the past 5 years: cervical cancer *in situ*, and non-melanoma cancer of the skin. Patients with other cancers diagnosed within the past 5 years and felt to be at low risk of recurrence should be discussed with the study sponsor to determine eligibility.

3.2.13 Has received a live vaccine within 28 days of planned start of study therapy.

### **3.3 Inclusion of Women and Minorities**

Both men and women of all races and ethnic groups are eligible for this trial. The accrual targets will reflect the expected accrual over the life of the study.

### **3.4 Inclusion Criteria for Crossover Therapy**

3.4.1 ECOG performance status  $\leq 2$  (Karnofsky  $\geq 60\%$ , see Appendix A)

3.4.2 Participants must have normal organ and marrow function as defined below:

- absolute neutrophil count  $\geq 1,000/\text{mcL}$
- platelets  $\geq 75,000/\text{mcL}$
- total bilirubin  $\leq 1.5 \times$  institutional upper limit of normal (ULN) ( $\leq 1.5 \times$  institutional upper limit of normal (ULN) in patients with well documented Gilbert's Syndrome)
- AST(SGOT)/ALT(SGPT)  $\leq 3.0 \times$  institutional ULN ( $\leq 5.0 \times$  institutional ULN with documented liver metastases),

3.4.3 Female subjects of childbearing potential, as defined in section 3.1.14, must have either a negative urine or a negative serum pregnancy test within seven (7) days of first dose of pembrolizumab. If a urine test is positive or cannot be confirmed as negative, a serum pregnancy test will be required.

3.4.4 Participants with accessible disease must be willing to undergo a research biopsy before beginning crossover therapy.

### **3.5 Exclusion Criteria for Crossover Therapy**

3.5.1 Clinically significant electrocardiogram (ECG) abnormality, including a marked baseline prolonged QT/QTc ([QT interval/corrected QT interval], eg, a repeated demonstration of a QTc interval  $>500$  ms).

3.5.2 History or evidence of active, noninfectious pneumonitis that required treatment with steroids.

## 4. REGISTRATION PROCEDURES

### 4.1 General Guidelines for DF/HCC Institutions

Institutions will register eligible participants in the Clinical Trials Management System (CTMS) OnCore. Registrations must occur prior to the initiation of protocol therapy. Any participant not registered to the protocol before protocol therapy begins will be considered ineligible and registration will be denied.

Participants who are randomized, but do not initiate study treatment will be replaced.

The following registration/randomization procedures should be followed:

- An investigator will confirm eligibility criteria and a member of the study team will complete the protocol-specific eligibility checklist.
- The eligibility checklist(s) and all pages of the consent form(s) will be faxed to the ODQ at [contact].
- The ODQ Registrar will (a) review the eligibility checklist, (b) register the participant on the protocol, and (c) randomize the participant.
- An email confirmation of the registration and/or randomization will be sent to the Overall PI, study coordinator(s) from the Lead Site
- Prior to beginning crossover therapy, the crossover eligibility section of the checklist should be completed and signed by the treating investigator and re-faxed to the ODQ at [contact]. The ODQ registrar will review the eligibility checklist, change the subject's treatment arm, and notify the study team.

Following registration, participants may begin protocol therapy. Issues that would cause treatment delays should be discussed with the Overall Principal Investigator (PI). If a participant does not receive protocol therapy following registration, the participant's registration on the study must be canceled. Registration cancellations must be made in OnCore as soon as possible.

### 4.2 Registration Process for DF/HCC Institutions

DF/HCC Standard Operating Procedure for Human Subject Research Titled *Subject Protocol Registration* (SOP #: REGIST-101) must be followed.

#### **4.3 General Guidelines for Other Investigative Sites**

Not applicable

#### **4.4 Registration Process for Other Investigative Sites**

Not applicable

### **5. TREATMENT PLAN**

#### **5.1 Treatment Regimen**

This is a phase 2 study of treatment with eribulin mesylate +/- pembrolizumab, in metastatic HR-positive breast cancer. Eighty-eight participants will be randomized (1:1) to eribulin mesylate with pembrolizumab (Arm A) or eribulin mesylate (Arm B). Participants randomized to eribulin mesylate monotherapy will have the option to receive pembrolizumab monotherapy at time of progression but they must meet the criteria in section 5.2.3 and begin treatment within 2 months of progression to crossover. Eribulin mesylate will be administered on days 1 and 8 of each 21 day cycle. Pembrolizumab will be administered on day 1 of each 21 day cycle. If treatment is delayed, all protocol required assessments will be delayed accordingly.

Treatment will be administered on an outpatient basis. Reported adverse events and potential risks are described in Section 7. Appropriate dose modifications are described in Section 6. Details of the regimen are described in Table 1/2. No investigational or commercial agents other than those described below may be administered with the intent to treat the participant's malignancy.

Treatment regimen is described in Table 1 (Arm A) and in Table 2 (Arm B).

**Table 1: Regimen description- ARM A**

Regimen Description					
Agent	Premedication ; Precautions	Dose	Route	Schedule	Cycle Length
Pembrolizumab	Not routinely necessary unless prior infusion reaction.	200mg- iv	IV over approximately 30 minutes (range: 25-40 minutes). Infuse prior to starting eribulin mesylate infusion.	Day 1, q3w	21 days (3 weeks)

Eribulin mesylate	No routine premedication required	1.4 mg/m  D1 and D8iv*	IV, 2-5 minutes. May be administered diluted in 100 mL normal saline.	Days 1 and 8, iv	21 day (3 weeks)
-------------------	-----------------------------------	---------------------------------------	--	------------------	------------------

\*Dose reductions may be made as per Tables 4-7. Further details about dose reductions can be found in Section 6.

**Table 2: Regimen description- ARM B**

**Regimen Description**

Agent	Premedication ; Precautions	Dose	Route	Schedule	Cycle Length
Eribulin mesylate	No routine premedication required	1.4 mg/m  * iv	IV, 2-5 minutes. May be administered diluted in 100 mL normal saline.	Days 1 and 8, iv *	21 day (3 weeks)

\*Dose reductions may be made as per Tables 6-7. Further details about dose reductions can be found in Section 6.

*Note: After progression patients who wish can receive pembrolizumab 200mg, at a final concentration of 1 mg/mL to 10 mg/mL in NS or D5, every 21 days. Pembrolizumab should be administered as described in Arm A, pre-treatment criteria will also follow what is recommended in Arm A.*

## 5.2 Pre-Treatment Criteria, Treatment, end off treatment and follow up visits

### 5.2.1 Cycle 1, Day 1

**Criteria to treat at cycle 1 day 1:**

- Absolute neutrophil count  $\geq 1500/\text{mcL}$
- Platelets  $\geq 100,000/\text{mcL}$
- ALT and AST  $\leq 2.5 \times \text{ULN}$  in a patient with no documented liver metastases; ALT and AST  $\leq 5.0 \times \text{ULN}$  in a patient with documented liver metastases
- Total bilirubin  $\leq 1.5 \times \text{ULN}$  ( $2.0 \times \text{ULN}$  in a patient with well documented Gilbert's syndrome)

## 5.2.2 Day 8 and Day 1 of subsequent cycles (including C1D1 and beyond of Crossover)

### **Criteria to treat at day 8 and day 1 of subsequent cycles:**

- **Absolute neutrophil count  $\geq 1000/\text{mcL}$**
- **Platelets  $\geq 75,000/\text{mcL}$**
- **ALT and AST  $\leq 3.0 \times \text{ULN}$  in a patient with no documented liver metastases; ALT and AST  $\leq 5.0 \times \text{ULN}$  in a patient with documented liver metastases**
- **Total bilirubin  $\leq 1.5 \times \text{ULN}$  (2.0  $\times \text{ULN}$  in a patient with well documented Gilbert's syndrome)**

## 5.3 Agent Administration

### 5.3.1 Pembrolizumab

Pembrolizumab will be administered by trained medical personnel at the investigational site. Treatment compliance will be monitored through documentation of study treatment administration in the subject's medical record.

Pembrolizumab will be administered in clinic on day 1 (+/- 3 days) of each cycle. It will be administered as a 30 minute IV infusion. Sites should make every effort to target infusion timing to be as close to 30 minutes as possible. However, given the variability of infusion pumps from site to site, a window of -5 minutes and +10 minutes is permitted (i.e., infusion time is 25-40min).

Pembrolizumab should be administered prior to eribulin mesylate administration. There should be no overlap in timing of the two administrations.

### 5.3.2 Eribulin mesylate

Eribulin mesylate will be administered by trained medical personnel at the investigational site. Treatment compliance will be monitored through documentation of study treatment administration in the subject's medical record.

Please refer to the FDA-approved package insert for eribulin mesylate for product information and a comprehensive list of adverse events.

Eribulin mesylate will be administered on Days 1 and 8 of each 21-day cycle Day 8 Eribulin mesylate administration may occur at DFCI Milford, as needed.

Eribulin mesylate will be dosed per institutional guidelines.

## 5.4 Discontinuation of pembrolizumab and Second Course Phase (Retreatment Period)

If pembrolizumab is stopped for toxicity, participants are permitted to continue on protocol therapy with eribulin mesylate alone.

Participants may elect to stop pembrolizumab and eribulin mesylate with SD, PR or CR after at least 27 weeks of treatment and having had at least two treatments with pembrolizumab after documentation of the SD or response.

Subjects who stop pembrolizumab in these conditions may be eligible additional pembrolizumab therapy if they progress after stopping study treatment. This retreatment is termed the Second Course Phase of this study and is only available if the study remains open and the subject meets the following conditions:

- Stopped initial treatment with pembrolizumab after attaining an investigator-determined confirmed SD, PR or CR according to RECIST 1.1, and
  1. Was treated for at least 27 weeks with pembrolizumab before discontinuing therapy
  2. Received at least two treatments with pembrolizumab beyond the date when the initial SD or response was declared

**OR**

- Had SD or response and stopped pembrolizumab treatment after 27 weeks of study therapy for reasons other than disease progression or intolerance.

Subjects who restart treatment will be retreated at the same dose and dose interval as when they last received pembrolizumab. Visit requirements are as outlined for subjects on the initial treatment phase of the trial.

## **5.5 Discontinuation of eribulin mesylate**

If eribulin mesylate is stopped for toxicity, participants are permitted to continue on therapy with pembrolizumab alone.

## **5.6 General Concomitant Medication and Supportive Care Guidelines**

### **5.6.1 Concomitant Medication Guidelines**

Medications or vaccinations specifically prohibited in the exclusion criteria are not allowed during the ongoing trial. If there is a clinical indication for one of these or other medications or vaccinations specifically prohibited during the trial, discontinuation from trial therapy or vaccination may be required. The investigator should discuss any questions regarding this with the Merck Clinical team. The final decision on any supportive therapy or vaccination rests with the investigator and/or the subject's primary physician.

#### Acceptable Concomitant Medications

All treatments that the investigator considers necessary for a subject's welfare may be administered at the discretion of the investigator in keeping with the community standards of medical care. All concomitant medication will be recorded on the case report form (CRF) including all prescription, over-the-counter (OTC), herbal supplements, and IV medications and fluids. If changes occur during the trial period, documentation of drug dosage, frequency, route, and date may also be included on the CRF.

All concomitant medications received within 28 days before the first dose of trial treatment and 30 days after the last dose of trial treatment should be recorded. Concomitant medications administered after 28 days after the last dose of trial treatment should be recorded for SAEs as specified in Section 7.2.

#### Prohibited Concomitant Medications

Subjects are prohibited from receiving the following therapies during the Screening and Treatment Phase of this trial:

- Antineoplastic systemic chemotherapy or biological therapy
- Immunotherapy not specified in this protocol
- Chemotherapy not specified in this protocol
- Biologic or targeted agents not specified in this protocol
- Investigational agents other than pembrolizumab
- Radiation therapy
- Any systemically active oral, injected, or implanted hormonal method of contraception except for progesterone coated intrauterine devices (IUDs) that had been previously implanted.
- Estrogen replacement therapy.
- Live vaccines within 28 days prior to the first dose of trial treatment and while participating in the trial. Examples of live vaccines include, but are not limited to, the following: measles, mumps, rubella, varicella/zoster, yellow fever, rabies, BCG, and typhoid vaccine.
- Systemic glucocorticoids for any purpose other than to modulate symptoms from an event of clinical interest of suspected immunologic etiology. The use of physiologic doses of corticosteroids (10 mg prednisone by mouth daily or equivalent) is allowed..
- Care should be taken with concomitant use of strong CYP3A4 inhibitors/inducers (e.g., ketoconazole and itraconazole; see Appendix B) and eribulin mesylate. An alternate medication with no or minimal potential to inhibit CYP3A4 should be considered. If a strong CYP3A4 inhibitor is co-administered with eribulin mesylate, patients should be closely monitored for adverse reactions.

Subjects who, in the assessment by the investigator, require the use of any of the aforementioned treatments for clinical management should be removed from the trial. Subjects may receive other medications that the investigator deems to be medically necessary.

There are no prohibited therapies during the Post-Treatment Follow-up Phase.

#### 5.6.2 Supportive Care Guidelines – general medications

The following treatments are permitted throughout the duration of the study treatment phase and during follow-up:

- Standard therapies for pre-existing medical conditions unless listed as prohibited therapy below. Any medication intended solely for supportive care (e.g., analgesics, anti-diarrheal, anti-depressants) may be used at the investigator's discretion. Antiemetics and anti-diarrheal medications should not be administered prophylactically before initial treatment with study drugs. At the discretion of the investigator, prophylactic antiemetic and anti-diarrheal medication(s) may be used as per standard clinical practice before subsequent doses of study drugs.
- Hematopoietic growth factors (e.g., G-CSF, granulocyte macrophage colony stimulating factor) may be used at investigator's discretion for the primary prophylaxis and/or management of treatment-emergent neutropenia and/or for secondary prophylaxis as per NCCN/European Society for Medical Oncology guidelines  or local standard practice. However, treatment with granulocyte-colony stimulating factors will not be permitted in cycle 1 unless the patient has febrile neutropenia and the physician considers its use as clinically indicated. It will be left to the treating physician choice from cycle 2.
- Bisphosphonate or denosumab therapy to be used in accordance with the approved labeled indication and/or nationally recognized treatment guidelines. Participants already receiving bisphosphonate/denosumab at the time of study entry can continue the treatment.
- Anticoagulants - Anticoagulation with heparin, heparin derivatives, and/or warfarin may be given at the discretion of the treating physician. Coagulation parameters should be checked at least once monthly, or more frequently at discretion of treating physician.
- Pain medications administered per standard clinical practice are acceptable while the patient is enrolled in the study.

Patients who experience toxicities should be treated symptomatically as clinically indicated. Medications that are considered necessary for the subject's welfare and that are not expected to interfere with the evaluation of study treatment or be restricted may be given at the discretion of the investigator. Ancillary treatments will be given as medically indicated.

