**Table 7. Dose adjustments for Eribulin Mesylate**

Adverse reaction/Toxicity	Grade/Details	Eribulin mesylate dose modification
ANC	< 500 cells/mm  lasting > 7 days with or without use of growth factors	Hold eribulin mesylate until recovery to grade $\leq 2$ and reduce by 1 dose level. Prophylactic growth factor support should be instituted for subsequent cycles.
	< 500 cells/mm  lasting $\leq 7$ days without use of growth factors	Hold eribulin mesylate until recovery to grade $\leq 2$ . Resume eribulin mesylate at the same dose. Growth factor support should be provided.
	< 500 cells/mm  lasting $\leq 7$ days in despite use of growth factors	Hold eribulin mesylate until recovery to grade $\leq 2$ , and reduce by 1 dose level. Continue ongoing prophylactic growth factor support for subsequent cycles.
	<1000 /mm  with fever or infection without use of growth factors	Hold eribulin mesylate until recovery to grade $\leq 2$ . Resume eribulin mesylate at the same dose. Growth factor support should be provided.
	<1000 /mm  with fever or infection despite use of growth factors	Hold eribulin mesylate until recovery to grade $\leq 2$ , and reduce by 1 dose level. Growth factor support should be provided.
	<1000 /mm  without fever or infection	First occurrence: Hold eribulin mesylate until recovery to grade $\leq 2$ then resume at the same dose. Growth factor support should be provided .  If uncomplicated neutropenia (<1000 /mm  without fever or infection) occurs/recurs despite growth factor support, then hold eribulin mesylate until recovery to grade $\leq 2$ . Eribulin mesylate may be then be resumed at the same dose with growth factor support, or it may be reduced by one dose level.  If a patient misses two consecutive Day 8 eribulin mesylate doses due to uncomplicated neutropenia, then hold eribulin mesylate until recovery to grade $\leq 2$ , reduce by 1 dose level, and consider

		prophylactic growth factor support for subsequent cycles.
Platelets	Grade 2	Hold eribulin mesylate until recovery to grade $\leq 2$
	Grade 3	Hold eribulin mesylate until recovery to grade $\leq 2$ then reduce by 1 dose level.
	Grade 4	Hold eribulin mesylate until recovery to grade $\leq 2$ then reduce by 1 dose level.
Anemia	Grade 4	Hold eribulin mesylate until recovery to grade $\leq 2$ then reduce by 1 dose level. PRBC transfusions are permitted to treat anemia on protocol.

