Peripheral neuropathy	Grade 2	For intolerable (as determined by physician and patient) grade 2, decrease eribulin mesylate by one dose level.
	Grade 3	Hold eribulin mesylate until recovery to grade $\leq 2$ then reduce by 1 dose level.
	Grade 4	Permanently discontinue eribulin mesylate
Non-hematologic toxicity	Grade 3, first occurrence	Hold eribulin mesylate until recovery to grade $\leq 2$ . Maximize supportive care measures. If symptom recovery occurs within 1 week, then eribulin mesylate may be resumed at the same dose if deemed appropriate by the investigator, otherwise, reduce by 1 dose level.
	Grade 3, despite maximal supportive measures	Hold eribulin mesylate until recovery to grade $\leq 2$ then reduce by 1 dose level.
	Grade 4	Hold eribulin mesylate until recovery to grade $\leq 2$ then reduce by 1 dose level.
ANC = absolute neutrophil count		

 
Toxicities graded in accordance with National Cancer Institute Common Toxicity Criteria for AEs, version 4.0
 
Discontinuation should be considered if a dose reduction to <math><0.7 \text{ mg/m}^2</math> is required.
 
A minimum of 6 days between D1 and D8 of eribulin mesylate administration will be required and a minimum of 10 days between D8 and D22 (i.e. D1 of next cycle) will be required.
 
If a patient does not meet criteria to receive Day 8 of eribulin mesylate, the investigator may decide to make up the dose on Day 15 of the cycle. If the Day 15 dose is given, the next cycle should not be initiated until 2 weeks later. If the Day 15 dose is held again, the next cycle may initiate the following week.
 
Once a dose is reduced, it should not be re-escalated.
 
Treatment with eribulin mesylate will be discontinued if participants require a delay greater than 3 weeks.
 
Treatment with pembrolizumab is allowed to continue if eribulin mesylate is discontinued.
 
		

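### Section 5.6.2 bars G-CSF in cycle 1 outside febrile neutropenia, but two non-febrile neutropenia rows of Table 7 call for growth factor support with no cycle 1 exception

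*Combined protocol and SAP*

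**What the plan says.** Section 5.6.2 (Supportive Care Guidelines) opens with a general permission: growth factors may be used at the investigator's discretion "for the primary prophylaxis and/or management of treatment-emergent neutropenia". It then makes an exception: "treatment with granulocyte-colony stimulating factors will not be permitted in cycle 1 unless the patient has febrile neutropenia" and the physician considers it clinically indicated. After that, "It will be left to the treating physician choice from cycle 2".

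Table 7 in section 6.2 (dose adjustments for eribulin) gives instructions by neutrophil count. For ANC below 500 lasting 7 days or less without growth factors, eribulin is held until recovery, and then: "Resume eribulin mesylate at the same dose. Growth factor support should be provided". For the first ANC below 1000 without fever or infection, eribulin is held until recovery, "then resume at the same dose. Growth factor support should be provided". Neither row mentions cycle 1 or refers to section 5.6.2. By contrast, for ANC below 500 lasting more than 7 days the table says "Prophylactic growth factor support should be instituted for subsequent cycles".

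A note under Table 7 covers a Day 8 dose that cannot be given: "the investigator may decide to make up the dose on Day 15 of the cycle". Section 6 and the same notes rule out raising the eribulin dose again once it has been reduced.

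**The concern.** A patient without fever whose neutrophils fall in cycle 1 comes under two instructions. One does not permit G-CSF in that cycle. The other says growth factor support should be given and sets no cycle limit. A site that gives it in cycle 1 departs from section 5.6.2. A site that withholds it departs from Table 7, unless Table 7 is read as deferring support to the next cycle, which these rows do not say.

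Two things are at stake. The first is consistent safety management of neutropenia, which section 2.4 lists among the most common eribulin toxicities. The second is eribulin exposure: some Table 7 rows for later events depend on whether growth factor was in use at the time, and a reduction is permanent.

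**Working it through.** No arithmetic applies; the check sets the two sections side by side.

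**Step 1: which ANC rows of Table 7 meet the cycle 1 bar.**

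| Table 7 situation | Eribulin after recovery | Growth factor instruction | Against section 5.6.2 in cycle 1 |
|---|---|---|---|
| ANC <500, >7 days, with or without growth factor | Reduce one level | In later cycles | No conflict |
| ANC <500, ≤7 days, no growth factor | Same dose | To be provided; no cycle limit | **Conflict if no fever** |
| ANC <500, ≤7 days, despite growth factor | Reduce one level | Continue in later cycles | Presupposes prior use |
| ANC <1000, fever or infection, no growth factor | Same dose | To be provided; no cycle limit | Fever is within the exception; infection without fever is not clearly within it |
| ANC <1000, fever or infection, despite growth factor | Reduce one level | To be provided | Presupposes prior use |
| ANC <1000, no fever or infection, first time | Same dose | To be provided; no cycle limit | **Conflict** |
| ANC <1000, no fever or infection, despite growth factor | Same dose with growth factor, or reduce | As in previous column | Presupposes prior use |
| Two consecutive Day 8 doses missed | Reduce one level | Consider for later cycles | Cannot be completed in cycle 1 |

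Two rows conflict and a third is unclear for infection without fever. Three ANC entries place growth factor in later cycles, so the table states that limit where it intends it. Silence in the two conflicting rows cannot safely be read as the same limit.

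**Step 2: can the situation arise wholly within cycle 1?** Yes.

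- The study calendar (section 10) schedules a hematology panel on Day 8 of cycle 1.
- Section 5.2.2 requires ANC of at least 1000 to treat on Day 8. A patient without fever who is below that is held and falls into the first-occurrence row.
- The note under Table 7 allows the dose to be made up on Day 15. Hold, support and resumption can therefore all precede cycle 2.

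**Step 3: what follows for the eribulin dose.** Both conflicting rows resume eribulin at the same dose, so the choice between sections does not change the dose after the first event. A difference needs a further event while growth factor use differs. Suppose two patients have the same cycle 1 event and a Day 15 make-up dose, one with growth factor (following Table 7) and one without (following section 5.6.2). If each then has ANC below 500 for 7 days or less, the first is reduced one level (from 1.4 to 1.1 mg/m² in Table 6) and the second resumes at 1.4 mg/m². The reduction cannot be reversed.

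**The case against.** The strongest reply is that a site can satisfy both sections. In the two rows, growth factor support comes after hold, recovery and resumption, and the Day 15 dose is optional. If it is not given, eribulin resumes on Day 1 of cycle 2, where section 5.6.2 leaves G-CSF to the physician. Section 5.6.2 is also the only text that speaks to cycle 1 specifically, so it could be taken to limit the general table. Further, Table 7 uses the softer verb and says growth factor, where section 5.6.2 names G-CSF.

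Part of this stands. The conflict is confined to cycle 1, and within it to support given during the hold or with a Day 15 dose. It would go too far to say that sites can never comply with both. But no passage states that Table 7 support waits for cycle 2, that section 5.6.2 overrides the table, or that another growth factor is meant. Each reading is one that a site must supply for itself, and different sites may supply different ones.

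A reader might also infer that section 5.6.2 contradicts itself by allowing primary prophylaxis and then barring G-CSF in cycle 1. It does not: it states a general rule followed by an explicit exception.

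**Conclusion.** The contradiction is real and narrow. For a patient with non-febrile neutropenia in cycle 1, two Table 7 rows call for support that section 5.6.2 does not permit in that cycle. A third row leaves infection without fever unclear. That these rows apply in cycle 1 is inferred from the absence of any cycle limit, supported by the limits stated in other rows.

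The consequence is that sites may manage neutropenia differently and, after a further event, may reach different eribulin doses. Not every reduction depends on growth factor use: ANC below 500 for more than 7 days leads to a reduction either way, as do two missed Day 8 doses. For recurrent uncomplicated neutropenia despite support, the reduction is optional.

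The number of patients affected cannot be derived. A reader might apply the 32% grade 4 neutropenia rate in section 2.4 to the 88 planned patients (0.32 × 88 ≈ 28), but that figure does not measure the conflict. It covers all cycles. It includes patients in the non-conflicting row for more than 7 days; section 2.4 reports grade 4 neutropenia of that duration in 12% of patients in the phase III trial. It also omits patients who reach only the ANC below 1000 row. It is neither an upper nor a lower bound.

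Nor do the documents support a claim of bias between arms. Both arms receive eribulin under the same rules, and no effect on the PFS comparison, power or type I error has been shown.

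**What to change.** Section 5.6.2 and the ANC rows of Table 7 must be reconciled for cycle 1. The sponsor's clinical team decides which instruction applies; this review takes no position on that. The reconciled text should settle three things and cross-refer between the two sections:

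- how the two non-febrile rows apply in cycle 1, both during a hold and with a Day 15 make-up dose;
- whether infection without fever falls within the cycle 1 exception;
- whether the growth factor support in Table 7 means the same agents as the G-CSF restriction in section 5.6.2.

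The cost is protocol wording. Sample size and the analysis plan are unaffected.
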